### 13.1.2. PRIMARY ANALYSIS OF PRIMARY EFFICACY VARIABLE(S)

The primary objective of this study is to test the hypothesis that there is a difference between either or both Cat-PAD treatment arms and the Placebo arm.

The primary efficacy analysis is to be performed for the FAS.

The least squares (LS) mean difference in mean CS between treatment arms, along with 95% two-sided CIs and p-value are to be estimated by fitting an analysis of covariance (ANCOVA) model, adjusting for the stratification factors listed in [Section 7.1: Adjustments for Covariates and Factors to be Included in Analyses](#).

Additionally, the LS mean and 95% CI for the CS at the CP007 study endpoint of PAC3 is to be calculated for the CP007A FAS subjects using the same ANCOVA. The LS mean and 95% CI is to be presented by treatment arm.

The Bonferroni-Holm procedure is to be utilised to assess each of the two treatment comparisons (two courses of Cat-PAD vs. Placebo and one course of Cat-PAD vs. Placebo), whereby the smallest p-value (of the two treatment comparisons) is to be tested at the 0.05/2 (i.e.  $p < 0.025$ ) alpha level. If this first comparison is statistically significant then the remaining treatment comparison p-value is to be tested at the 0.05 alpha level. The study is to be declared a success if one or more

---

Document: CP007A SAP.docx

Author: [name]

Version Number:

V 2.0

Version Date:

23 Feb 2017

Template No: CS\_TP\_BS016 – Revision 3

Reference: CS\_WI\_BS005

Effective Date: 01May2012

Copyright © 2012 Quintiles Transnational Corp. All rights reserved.

The contents of this document are confidential and proprietary to Quintiles Transnational Corp. Unauthorized use, disclosure or reproduction is strictly prohibited.

treatment arms are statistically significantly different from Placebo.

The differences in LS means for each treatment comparison of active vs. Placebo together with the corresponding two-sided 95% CI and the p-values are to be presented. Additionally p-values are to be calculated and presented for all model effects.

The ratio of LS means along with its 95% CI (calculated by using Fieller's method) is to be presented for evaluation of the clinical significance of active treatment vs. Placebo comparisons.

The primary efficacy variable is also to be analysed for subgroups as specified in [Section 7.5: Examination of Subgroups](#), using a simplified ANCOVA including treatment arm as main effect and Baseline CS as covariate. Subgroup analyses are not to utilize the Bonferroni-Holm procedure to assess each of the two treatment comparisons (two courses of Cat-PAD vs. Placebo and one course of Cat-PAD vs. Placebo). Each treatment comparison p-value is to be tested at the 0.05 alpha level.

Observed and change from Baseline values are to be summarised by descriptive statistics (n, mean, SD, median, minimum and maximum) for each annual Allergy Assessment Period and treatment arm.

A waterfall plot of the percentage change from Baseline in CS for each individual subject is to be plotted for each treatment arm.

The analyses are to be repeated for the mITT population.

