7.4.2.1 Primary Analysis

The primary efficacy variable for this study is the mean Combined Score (TRSS/8+AMS).

For the primary efficacy analysis, the data will be summarised and analysed using methods as for study CP007. The analysis will provide a comparison of the mean Combined Score (TRSS/8+AMS) for each treatment group. In addition, 95% Confidence intervals will be used to explore the size and direction of any differences between groups.

The statistical analysis will use covariates as used in CP007, including pooled centre, age group (as randomised), gender, asthma status and baseline score. Additional informative subgroup descriptive analyses may also be performed.

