### 6.3. STATISTICAL TESTS

All tests are two-sided, unless otherwise specified in the description of the analyses. The significance level for each analysis is specified in the relevant analysis section of the SAP.

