## 7.5. EXAMINATION OF SUBGROUPS

Subgroup analyses are to be conducted for the primary analysis of primary efficacy variable only. It should be noted that the study was not designed to detect treatment differences with high statistical power within subgroups. Subgroup analyses are only to be performed if there are at least 10 subjects in each category of the subgroup.

The following subgroups are to be assessed for the primary efficacy variable:

- Gender:
  - o Female
  - o Male
- Age (years):
  - o  $\geq 12$  to  $\leq 17$
  - o  $\geq 18$  to  $\leq 49$
  - o  $\geq 50$  to  $\leq 65$
  - o  $> 65$
- Ethnic group
  - o Caucasian
  - o Black
  - o Asian (Indian)
  - o Asian (Oriental)
  - o American Hispanic
- Asthma status

---

Document: CP007A SAP.docx

Author: [name]

Version Number:

V 2.0

Version Date:

23 Feb 2017

Template No: CS\_TP\_BS016 – Revision 3

Reference: CS\_WI\_BS005

Effective Date: 01May2012

Copyright © 2012 Quintiles Transnational Corp. All rights reserved.

The contents of this document are confidential and proprietary to Quintiles Transnational Corp. Unauthorized use, disclosure or reproduction is strictly prohibited.

- o Present
- o Absent

All subgroup variables above are from the same source as described in [Section 6.2](#): Baseline.

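### The SAP replaces the protocol's descriptive subgroup analyses with up to 26 unadjusted within-category tests and no interaction test, so the plan cannot show whether the effect differs between subgroups.

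*SAP*

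**What the plan says.** **Protocol.** Section 7.4.2.1, and the synopsis in the same terms, says only this about subgroups: "Additional informative subgroup descriptive analyses may also be performed".

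**SAP 7.5** makes them a planned analysis: "The following subgroups are to be assessed for the primary efficacy variable". It lists gender (2 categories), age (4, including over 65), ethnic group (5) and asthma status (2). It warns that "the study was not designed to detect treatment differences with high statistical power within subgroups" and sets a size rule: "Subgroup analyses are only to be performed if there are at least 10 subjects in each category of the subgroup".

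**SAP 13.1.2** gives the model, "using a simplified ANCOVA including treatment arm as main effect and Baseline CS as covariate", and the testing rule: "Subgroup analyses are not to utilize the Bonferroni-Holm procedure to assess each of the two treatment comparisons", followed by "Each treatment comparison p-value is to be tested at the 0.05 alpha level". The analyses are repeated in the mITT population. SAP 6.3 makes the tests two-sided.

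No treatment-by-subgroup term appears in either document. The SAP does not label the subgroup p-values exploratory, does not mention how many there are, and gives no reason for moving from description to testing.

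**The concern.** A p-value inside one category asks whether treatment beats placebo in that category. It does not ask whether the effect differs from that in another category, which is the usual purpose of a subgroup analysis. A significant result in women beside a non-significant one in men is compatible with the same effect in both.

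Two misreadings follow. If treatment works equally in everyone, small categories will mostly be non-significant and look like non-responders. If treatment does nothing, many unadjusted tests will sometimes produce an apparently responsive subgroup.

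The size rule is a separate weakness. It counts subjects over all arms, and it does not say whether a sparse category is omitted alone or takes its whole factor with it. Planned analyses of age or ethnic group may therefore not be run.

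**Working it through.** **1. The plan's own power figures.** Protocol 7.2 gives a difference of 0.525, SD 1.29 and two-sided alpha 0.025. Power ≈ Φ(0.525/SE − 2.241), with SE = 1.29·√(2/n).
- n = 266 per arm: SE = 0.1119, ratio 4.69, power 99.3% (stated: at least 99%).
- n = 130 per arm: SE = 0.1600, ratio 3.28, power 85.1% (stated: at least 80%).

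Both are reproduced. The documents state no subgroup power or error rate.

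**2. Power inside a category.** Same difference and SD, two-sided 0.05, two-sample t test. The category shares are assumptions.

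| Category | Per arm | Power |
|---|---|---|
| 40% of 266 | 106 | 84% |
| 10% of 266 | 27 | 31% |
| 3% of 266 | 8 | 12% |
| 10 subjects over three arms | about 3 | 7% |

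A category of 10% or less would usually be non-significant even if the full planned effect were present.

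**3. Number of tests.** 2 + 4 + 5 + 2 = 13 categories; 13 × 2 comparisons = 26 tests per population per year. Expected false positives with no true effect: 26 × 0.05 = 1.3.

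**4. Chance of at least one p<0.05 when there is no effect.** If the k tests were independent, it is 1 − 0.95^k. They are not: the two comparisons share a placebo arm, and every subject appears under all four factors. The last column therefore simulates three equal arms with an ANCOVA on arm and baseline in each category, for the FAS in one year. Main assumed shares: gender 60/40; age 10/70/18/2%; ethnic group 85/6/3/3/3%; asthma 45/55; baseline correlation 0.5.

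| Categories tested | k | Independent | Simulated |
|---|---|---|---|
| All or nearly all, total N 798-1398 | 26 | 73.6% | 61-65% |
| N 390 (130 per arm), only sparse categories dropped | at most 26 | – | 56-58% |
| N 390, a sparse category cancels its factor | at most 26 | – | 39-41% |
| Gender, asthma, three-level age | 14 | 51.2% | 42% |
| Gender and asthma only | 8 | 33.7% | 27-28% |

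The ranges at N 390 cover a second assumed mix (gender 50/50, age 10/65/23/2%, asthma 40/60). Adding the mITT repeat, with 70-90% of subjects retained, raises the first row to 72-78% and the last to 33-40%. Counting only false benefit, the first row falls to about 35-37%.

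**5. The size rule.** P(fewer than 10 subjects) for a category with share p, binomial:
- N = 798: 72% at p = 1%; 4.3% at 2%; 0.04% at 3%.
- N = 390: 74% at p = 2%.

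Whether a factor survives thus depends heavily on shares that the documents do not give. SAP 7.5 has an over-65 category, but the age groups in SAP 11 stop at 65, so that category may be nearly empty. Losing the age factor would leave 26 − 8 = 18 tests. SAP 5.2 re-assesses the FAS each year, so the set of factors analysed could also change from year to year.

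**6. After the fix.** Four interaction tests at 0.05: 1 − 0.95⁴ = 18.5% (simulated 19%). At 0.0125 each: 1 − 0.9875⁴ = 4.9%.

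**The case against.** The best defence is that these p-values decide nothing. SAP 13.1.2 rests success on the overall comparisons under Bonferroni-Holm. The factors are pre-specified and limited to the primary variable, low power is admitted, and the absence of adjustment is stated openly. Protocol 7.4 also leaves the nature of formal testing to the SAP. All of this stands, and it limits the consequence to how subgroup results are read. It does not supply a test of whether effects differ.

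A reader might infer more than the documents support:
- **That a false subgroup finding is more likely than not.** This holds only with no true effect, nearly all categories tested, and errors in either direction counted. At 130 per arm, with whole factors cancelled, the figure is about 40%.
- **That the 10-subject rule adds false positives.** It can only remove tests. Its faults are ambiguity and poor precision.
- **That a factor will probably be cancelled.** The 72% above needs a 1% category; at the 2% used in the simulation it is 4.3% at N = 798. No category counts are given.
- **That the error accumulates over four years.** SAP 4 analyses later years only after a positive outcome, so the years cannot simply be added.
- **That the primary type I error is inflated.** Subgroup results play no part in the success rule.

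**Conclusion.** The concern holds in this limited form. The SAP goes from description to unadjusted testing without giving a reason, and the tests it chooses cannot answer whether the effect varies. That defect needs no assumption about category sizes.

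The false-positive size does need one. Under the global null it lies between about 28% and 65% per population and year, depending on how many categories qualify and how the size rule is read. The shares and the baseline correlation are assumed throughout.

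The size rule is a separate, smaller defect: about three subjects per arm at its limit, and unclear on whether a category or a factor is dropped. This should be corrected, but it does not threaten the primary conclusion.

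**What to change.** 1. In SAP 13.1.2, remove the within-category tests at 0.05. Report each category's estimate with its 95% CI, labelled descriptive, in line with the protocol.
2. Add one treatment-by-subgroup interaction test per factor, one factor at a time, to the primary ANCOVA. Gender and asthma status are already main effects there (SAP 7.1). Ethnic group is not, and age enters only as adolescent or adult, so the ethnic-group and four-level age main effects must be added as well.
3. Label the interaction tests exploratory.
4. In SAP 7.5, state the minimum size per category and per arm, and say that only the sparse category is omitted or merged (for example, over 65 with 50 to 65). The threshold is the team's choice. Ten per arm would still give only about 14% power for a difference of 0.525, so it is a floor for showing an estimate and no basis for testing.

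**Cost.** SAP wording and four extra models, with no new data and no change to the primary analysis. Interaction tests have low power, so a non-significant one does not show that effects are equal. Four of them at 0.05 still carry about a 19% chance of a false signal.

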### **13.1.3. SENSITIVITY ANALYSIS OF PRIMARY EFFICACY VARIABLE(S)**

For sensitivity analyses the mean of the daily CS during the annual Allergy Assessment Period is to be calculated after imputation of the missing daily CS using the following three methods respectively:

- If valid data for any given day in the 3-week period is not available for a particular subject for a particular day, the previous day's CS (if complete) is to be carried forward by using Last Observation Carried Forward (LOCF) to impute the missing value. If the previous day's CS is not complete, the most recent complete CS is to be used.
- For a worst-case sensitivity analysis (WOCF), missing CS data for a particular day is to be imputed as the worst (highest) CS in the 3-week assessment period for that subject.
- Baseline Observation Carried Forward (BOCF) imputation of missing daily CS using the Baseline mean daily CS.

---

Document: CP007A SAP.docx

Author: [name]

Version Number:

V 2.0

Version Date:

23 Feb 2017

Template No: CS\_TP\_BS016 – Revision 3

Reference: CS\_WI\_BS005

Effective Date: 01May2012

Copyright © 2012 Quintiles Transnational Corp. All rights reserved.

The contents of this document are confidential and proprietary to Quintiles Transnational Corp. Unauthorized use, disclosure or reproduction is strictly prohibited.

For each annual assessment period all 21 days of symptom score recording is to be populated using each of the 3 methods detailed above, that is, if a subject has less than 21 days of valid symptom scores, the CS is to be populated for the full period of 21 days.

Using the imputed data (from each imputation method respectively) the LS mean difference in mean CS between treatment arms, along with 95% two-sided CIs and p-value are to be estimated using the same ANCOVA as for the primary efficacy variable as described in [Section 13.1.2: Primary Analysis of Primary Efficacy Variable](#).

As an additional sensitivity efficacy analysis of the primary efficacy variable the missing at random (MAR) assumption will hold for daily CS and the treatment effect is to be estimated using a Mixed Model Repeated Measures (MMRM) of the CS at each day of the annual Allergy Assessment Period, for the FAS and mITT populations.

In MAR the probability of an observation being missing depends only on observed measurements. This assumption implies that the behaviour of the missing observations can be predicted from the observed variables, and therefore a response can be estimated without bias using exclusively the observed data without any imputation of the missing days.

The MMRM will include all stratification factors as specified in [Section 7.1: Adjustments for Covariates and Factors to be Included in Analyses](#).

The following covariance structures will be used to estimate the within-patient errors in preliminary analyses:

- Unstructured
- Spatial power
- Heterogeneous Toeplitz
- Heterogeneous compound symmetric
- Simple structures with and without heterogeneous variances by visit

A different covariance structure is to be used for each treatment group if deemed appropriate. This is to be tested by fitting each of the aforementioned covariance structures, with- and without a GROUP statement where GROUP = treatment (see SAS code below). The covariance structure converging to the best fit, as determined by Akaike's information criterion (AIC) (covariance structure with the lowest value), is to be selected as the covariance structure for the primary analysis. Type III sum-of-squares for the LS means is to be used.

The following SAS code is to be used:

```
PROC MIXED data= IC INFO METHOD = TYPE3;  
  CLASS subject treatment pooled_site age_group gender asthma_status;  
  MODEL CS = baseline treatment pooled_site age_group gender asthma_status /
```

---

Document: CP007A SAP.docx

Author: [name]

Version Number:

V 2.0

Version Date:

23 Feb 2017

Template No: CS\_TP\_BS016 – Revision 3

Reference: CS\_WI\_BS005

Effective Date: 01May2012

Copyright © 2012 Quintiles Transnational Corp. All rights reserved.

The contents of this document are confidential and proprietary to Quintiles Transnational Corp. Unauthorized use, disclosure or reproduction is strictly prohibited.

**DDFM** = kr;  
**ESTIMATE** 'Cat-PAD2 vs Placebo' treatment 1 0 -1 / **CL**;  
**REPEATED** day / **SUBJECT**=subject /\***GROUP**=treatment\*/  
**TYPE**= <covariance structure option>;

**RUN**;

Appropriate ESTIMATE statements will be added for the comparisons of Cat-PAD1 vs Placebo as well as Cat-PAD2 vs Cat-PAD1.

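### SAP 13.1.3: the prescribed PROC MIXED code cannot run the MMRM sensitivity analysis it describes, because METHOD=TYPE3 maximises no likelihood for the AIC rule and day is missing from CLASS

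*SAP*

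**What the plan says.** SAP 13.1.3 describes three single-imputation sensitivity analyses (LOCF, WOCF, BOCF) and then a fourth: an MMRM of the daily Combined Score under a missing-at-random assumption, using observed days only, in the FAS and mITT.

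- **Candidates.** The list has five entries: unstructured, spatial power, heterogeneous Toeplitz, heterogeneous compound symmetric, and "Simple structures with and without heterogeneous variances by visit". The last entry covers two structures, so there are six. On treatment-specific covariance the SAP says "This is to be tested by fitting each of the aforementioned covariance structures, with- and without a GROUP statement where GROUP = treatment".
- **Choice.** "The covariance structure converging to the best fit, as determined by Akaike's information criterion (AIC", with the lowest value chosen, "is to be selected as the covariance structure for the primary analysis". The sentence after that calls for Type III sums of squares in connection with the LS means.
- **Code.** The SAP makes the code mandatory. It opens "PROC MIXED data= IC INFO METHOD = TYPE3" and continues "CLASS subject treatment pooled_site age_group gender asthma_status". It asks for Kenward-Roger degrees of freedom, has day as the REPEATED effect within subject, and has no RANDOM statement. Only the dataset name and the covariance option are placeholders. GROUP is commented out so that it can be switched on.
- **Contrast.** One ESTIMATE line is written out, "Cat-PAD2 vs Placebo' treatment 1 0 -1". For the others: "Appropriate ESTIMATE statements will be added for the comparisons of Cat-PAD1 vs Placebo as well as Cat-PAD2 vs Cat-PAD1".

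**The concern.** The covariance rule needs a maximised likelihood for every candidate, and the code names an estimation method that does not produce one. The code also indexes the repeated measures by a variable that it never declares as a class variable. A programmer who follows the SAP literally cannot deliver the described analysis. One who corrects the code departs from prescribed text without a record.

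At stake is the one sensitivity analysis that models the daily scores instead of filling in missing days. Protocol 7.4.2 expects missing data to matter for interpretation, so the code for this check should work as written.

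**Working it through.** The plan gives no figure on this point to reproduce. The check sets the code beside the rule and counts what the rule requires.

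**Inputs.** t = 21 daily scores per annual period (SAP 13.1.1); 3 treatment arms (SAP 3.1); 6 structures, each with and without GROUP = treatment; 2 populations (SAP 13.1.3).

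**Step 1: what the rule needs.** AIC = -2 log L + 2q, where L is the maximised (restricted) likelihood and q is the number of covariance parameters. Number of fits: 6 x 2 = 12 per population, and 12 x 2 = 24 per analysis year over FAS and mITT.

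| Structure | q | q at t = 21 | q with GROUP (x3) | Indexes discrete days |
|---|---|---|---|---|
| Unstructured | t(t+1)/2 | 231 | 693 | yes |
| Heterogeneous Toeplitz | 2t - 1 | 41 | 123 | yes |
| Heterogeneous compound symmetric | t + 1 | 22 | 66 | yes |
| Simple, heterogeneous variances | t | 21 | 63 | yes |
| Spatial power | 2 | 2 | 6 | no (numeric distance) |
| Simple | 1 | 1 | 3 | no |

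**Step 2: what METHOD=TYPE3 supplies.** It sets Type III mean squares equal to their expectations and solves for variance components. All model terms here are fixed effects and there is no RANDOM statement, so the residual mean square is the only one free of fixed effects. For covariance matrix V of all observations, its expectation is trace(QV)/df, with Q = I - X(X'X)⁻X'. That is one scalar equation. It can determine one unknown at most, and in the table only the simple structure without GROUP has q = 1. The other 11 candidates have from 2 to 693 parameters.

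**Step 3: the AIC.** Moment estimation maximises no likelihood. Even if the software printed a criterion evaluated at moment estimates, it would not be the AIC that the rule calls for. The missing-at-random argument in the same section, and the Kenward-Roger request, likewise presuppose a likelihood fit.

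**Step 4: CLASS.** The six declared variables are subject, treatment, pooled site, age group, gender and asthma status. Day is not among them. Four of the six structures attach a variance or covariance to each distinct day and so need day as a class variable. Spatial power needs day as a number. One variable cannot serve both uses, so a second copy is required.

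**Step 5: other text.** No other section of the SAP or protocol replaces the method or the CLASS list.

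The code was not run in SAS. The argument rests on what the method estimates, not on a particular error message.

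**The case against.** The strongest reply is that the block is a template and the intention is plain. The text names an MMRM under missing at random, lists the structures and chooses by AIC, and the code itself asks for information criteria and Kenward-Roger degrees of freedom. Only TYPE3 is out of line, and it probably came from the neighbouring sentence on Type III sums of squares. This largely stands. A reader might infer that the SAP leaves open whether TYPE3 or the AIC rule gives way, but the text points clearly to TYPE3. What does not stand is that the template status cures the defect: METHOD and CLASS are not placeholders, and the code is prescribed.

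A second reply is that little depends on this analysis, and that also stands. The primary ANCOVA already uses non-missing days without imputation (SAP 13.1.1 and 13.1.2), so an unimputed result exists in any case. The FAS is redefined each year and requires at least one recorded day (SAP 5.2). The MMRM therefore addresses missing days within a 21-day period, not drop-out between years.

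A reader might also infer that the contrast would report the wrong arm or a reversed sign. The documents do not show this. Appendix 1 lists placebo first under its presentation of treatment groups, but its table conventions put the study drug first. These are presentation rules and do not set the model's coding. SAP 13.1.2 names two courses before one course, each against placebo, which is compatible with coefficients 1 0 -1. The unstated level order and the undefined names Cat-PAD1 and Cat-PAD2 are missing detail, not an error.

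**Conclusion.** The point holds: the prescribed code cannot carry out the described MMRM. METHOD=TYPE3 cannot fit the multi-parameter structures or supply the 12 AIC values needed per population in each analysis year, and day is missing from CLASS for the four structures that index it. The count assumes that the last list entry is two structures and that its by-visit variances mean by day. It should not simply be multiplied by four years, because SAP 4 and 7.4 analyse later years only after a positive outcome.

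The scope is this one sensitivity analysis in the FAS and mITT. A reader might take the phrase about the primary analysis in the selection sentence to mean that the main result is affected. It is not: SAP 13.1.2 bases the primary analysis on an ANCOVA of the mean score, and SAP 13.1.3 and 13.1.4 call the MMRM a sensitivity analysis. No bias in the primary result is claimed, and the Bonferroni-Holm procedure and the power figures do not change. The code should still be corrected, because it is prescribed and the correction is easy.

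**What to change.** In SAP 13.1.3:

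1. Replace METHOD=TYPE3 with METHOD=REML. Keep Type III only as the type of test for fixed effects, and say so in the text.
2. Keep the lowest-AIC rule, restricted to structures that converge.
3. Add day to CLASS and create a separate numeric copy of day for the spatial power structure.

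As a tidy-up only:

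4. Define Cat-PAD1 and Cat-PAD2. State the treatment level order used in the model, or use LSMEANS differences by named level, so that each contrast matches its label.
5. In the selection sentence, name the MMRM sensitivity analysis in place of the primary analysis.

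Under SAP 4 a blinded team writes the programs and an independent statistician then applies the randomisation schedule, so the edit belongs before that hand-over. The cost is a text and code edit. Data collection, the primary analysis and the sample size do not change.
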